10.3.1. Demographic Data and Other Baseline Characteristics

10.3.1.1. Baseline Values

Baseline value of a variable is defined as the last available measurement of this variable before treatment (screening/pre-treatment data).

Age at entry will be computed from the date of birth to the informed consent (IC) date by the following formula:

$$Age (in years) = (IC date - the date of birth)/365.25.$$

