For each of the two stages of analysis (see Section 11 for details), the safety data gathered in that stage will be analyzed separately. That is, in the first stage analysis (acute + 12M follow-up), all AEs reported until the 12 months follow-up will be analyzed separately for the following sub-periods: 1) until the 12 weeks follow-up, 2) between the 12 weeks follow-up and the 12 months follow-up (including AEs from the first sub-period that are still ongoing), 3) combined until the 12 months follow-up. In the second stage analysis (24 months follow-up), all AEs reported between the 12 months follow-up and the 24 months follow-up (including AEs from the first stage that are still ongoing) will be analyzed. Furthermore, a combined analysis, including all reported AEs, will be provided at the end of the trial.

Central Laboratory Values

For all analyses involving data from the central laboratory only samples taken within the allowed time range are considered

- Pre procedure: Within 12 hours before start of the procedure until up to 15 min after start.
- Post procedure: Within 24 hours after end of the procedure

Samples not taken in the allowed time range are excluded from the analysis.

Imputation of data from the central laboratory is only done for planned missing values. Version 10.01 of the study protocol specifies some planned missing laboratory samples. On the one hand, a laboratory sample before the additional application of NexoBrid is not required. On the other hand, a laboratory sample before a nonsurgical procedure is only prescribed for the first eschar removal procedure and a laboratory sample after a nonsurgical procedure is only

required for the last eschar removal procedure. To enable analysis of pre-post differences on procedure level, the planned missing values are imputed as follows:

- Planned missing measurements before an additional application / a non-surgical procedure
 - Values of a sample taken after the previous eschar removal procedure are used if the laboratory sample was taken within 12 hours before start of the eschar removal procedure.
- Planned missing measurements after a non-surgical procedure
 Values of a sample taken before the subsequent eschar removal procedure are used if the laboratory sample was taken within 24 hours after end of the nonsurgical procedure.

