For each subject, each laboratory parameter and each time point of measurement a variable will be defined, indicating whether this measurement was post treatment potentially clinically significant high (pCS high) or post treatment potentially clinically significant low (pCS low).

From this, for each subject and each laboratory parameter, an indication whether this subject experienced any pCS high measurement post baseline in this parameter and/or whether this subject experienced any pCS low measurement post baseline in this parameter will be produced.

For the definition of pCS high and pCS low, see Section 13.2.2.

Vital Signs

Body temperatures given in °F will be transformed to °C using the following formula:

$$Temperature[°C] = \frac{5}{9}(Temperature[°F] - 32)$$

Differences in the vital signs assessments (body temperature, heart rate, respiratory rate, systolic blood pressure, diastolic blood pressure) between daily visits will be calculated by

$$Diff_d = VS_d - VS_{d-1}$$

where VS_d is the vital sign assessment at day d (daily follow-up) and d is varied from 2 to 7.

Note: Vital sign assessments will only be recorded while a subject is hospitalized. It may however be the case that certain subjects will be discharged during the first week, making some of the measurements not available. The respective subjects will be excluded from all vital sign analysis referring to time points after hospital discharge.

Additionally, for each subject, each vital sign and each time point of measurement a variable will be defined, indicating whether this measurement was post treatment potentially clinically significant high (pCS high) or post treatment potentially clinically significant low (pCS low) (based on definitions in Section 13.2.1). Baseline categories (pCS low, pCS high and not pCS) will be created using the reference values from Section 13.2.1 without the increase/decrease criteria.

In addition, for each subject and each vital sign an indication whether the subject experienced any pCS high and/or any pCS low result post baseline (within the first 7 days) in this vital sign will be produced.

For subjects discharged before day 7, this indication will be calculated only taking into account the time during hospitalization.

Pain Assessment

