11.1.5.5. Central Laboratory Values

Laboratory measurements obtained prior and after each eschar removal procedure as well as pre-post differences in laboratory values for each eschar removal procedure will be presented by treatment group using descriptive statistics. In addition, laboratory measurements obtained prior the first eschar removal procedure and after the last eschar removal procedure, as well as the corresponding pre-post difference, will be presented by treatment group using descriptive statistics.

As described in Section 10.3.6, laboratory values will be categorized as "abnormal (low)", "normal" and "abnormal (high)" based on the reference limits of the labs. This categorization will be analyzed by displaying counts and percentages of each category by treatment group and by procedure, as well as at the last eschar removal procedure, for each laboratory value separately.

Shift tables for central laboratory values indicating shifts from baseline to post every type of eschar removal procedure (first application, additional application, surgical procedure, additional surgical procedure, and nonsurgical procedure), as well as to post last eschar removal procedure, will be produced.

Furthermore, shift tables indicating shifts from baseline (low/normal/high) to any abnormal (low/high) value will be presented.

Additional tables will indicate shifts from baseline (low/normal/high) to any post treatment potentially clinically significant result. A listing of subjects experiencing such shifts will be provided.

The denominator for the shift tables will be the patients that had both pre and post results for the respective procedure.

The above tables will be presented for biochemistry parameters, hematology parameters and urine analysis parameters (where applicable) separately, and for parameters with numeric values only.

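### Central-laboratory samples outside the 12 h / 24 h window are dropped from every analysis with no count, listing or sensitivity analysis, and the window disagrees with the SAP's own baseline definition

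*SAP*

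**What the plan says.** SAP 10.3.4.4, under Central Laboratory Values, sets the scope: "For all analyses involving data from the central laboratory only samples taken within the allowed time range are considered". The two windows are "Pre procedure: Within 12 hours before start of the procedure until up to 15 min after start" and "Post procedure: Within 24 hours after end of the procedure". Anything else is removed: "Samples not taken in the allowed time range are excluded from the analysis". Replacement is narrow: "Imputation of data from the central laboratory is only done for planned missing values". A sample taken at the wrong time is not a planned missing value, so it is not replaced.

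The same section then builds a per-child flag over the post-treatment period, namely "an indication whether this subject experienced any pCS high measurement post baseline in this parameter", with a matching flag for low values. SAP 11.1.5.5 uses these results in shift tables to any abnormal and any pCS value, and lists the children with a pCS shift. It adds: "The denominator for the shift tables will be the patients that had both pre and post results for the respective procedure".

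The general baseline rule in SAP 10.3.1.1 carries no time limit: "Baseline value of a variable is defined as the last available measurement of this variable before treatment (screening/pre-treatment data").

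**The concern.** A time window is sensible when the quantity of interest is the change across one procedure. The any-abnormal and any-pCS tables ask a different question: did this child have a harmful value at any time after treatment began? Under a universal filter, the answer covers in-window samples only. A hemoglobin result 25 hours after a procedure would be in the database but in none of the planned central-laboratory tables, however abnormal it was.

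The pre-procedure limit raises a second problem. A sample taken 13 hours before treatment is rejected under 10.3.4.4, although 10.3.1.1 would accept it as baseline if it were the last one available. The child then has no pre value and leaves the shift table. SAP 13.2.2 describes the pCS thresholds in general as combining a value with a change from baseline, so losing the baseline can also leave some criteria undeterminable.

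The protocol synopsis rests the safety assessment mainly on adverse events and on clinically significant laboratory abnormalities. At stake is whether results that the trial already holds can be seen in the second of these.

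**Working it through.** The plan gives no figure for out-of-window samples, so there is nothing to reproduce. The check is mainly textual, with an illustrative range.

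**1. What the filter does to each output (SAP 10.3.4.4, 10.3.6, 11.1.5.5)**

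| Output | Late post sample (>24 h) | Early pre sample (>12 h), no other pre sample |
|---|---|---|
| Procedure-level pre-post difference | Lost, as intended | Lost, as intended |
| Post-procedure descriptive and low/normal/high tables | That value lost | In-window post value still counted; no pair is required |
| Shift table for a procedure | Child leaves if no other in-window post value exists for it | Child leaves |
| Any-abnormal and any-pCS shift tables, pCS listing | That value lost; child stays if other in-window samples exist | Depends on whether 10.3.4.4 overrides 10.3.1.1 |
| PTT/INR | Not affected (local laboratory) | Not affected |

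No table, listing or sensitivity analysis of the excluded samples is specified. The case-wise listing in SAP Section 11 covers variables not mentioned explicitly, so it cannot be relied on here.

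**2. The two baseline rules side by side**

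| Sample timing | 10.3.1.1 | 10.3.4.4 |
|---|---|---|
| 13 h before first procedure, last one available | Baseline | Excluded |
| 10 min after start of first procedure | Not before treatment, so not baseline | Accepted as pre-procedure |

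The SAP does not say which rule prevails. In the same section, pain has a stated fallback: the screening value is used when the pre-procedure value is missing. Central-laboratory values have none.

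**3. Window against schedule (SAP 7.1, Table 1)**

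- Pre sample: scheduled within 1 h before treatment. The window is 12 + 0.25 = 12.25 h.
- Post sample: scheduled at 4 h. The window ends 24 − 4 = 20 h later.
- Serum chemistry in children under 18 kg is collected at baseline only (footnote 2), so these children have no scheduled post-treatment chemistry whatever the window.

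**4. Illustration**

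Let *m* be the chance that a sample is out of window. It is assumed, the same for pre and post samples, and independent between them. Take N = 145 (SAP 13.3), with both samples due for every child.

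- No pre-post pair for one procedure: 145 × [1 − (1 − *m*)²]
- No in-window post sample over *k* procedures: 145 × *m*^*k*

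| *m* | No pair, one procedure | No post sample, *k* = 1 | No post sample, *k* = 2 |
|---|---|---|---|
| 2% | 145 × 0.0396 = 5.7 | 2.9 | 0.06 |
| 5% | 145 × 0.0975 = 14.1 | 7.25 | 0.36 |
| 10% | 145 × 0.19 = 27.6 | 14.5 | 1.45 |
| 20% | 145 × 0.36 = 52.2 | 29.0 | 5.8 |

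**5. Effect on a percentage**

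Take about 72 children per arm (145/2, assuming an even split) and 2 children with a pCS value, also assumed.

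- A flagged child stays in the table but the late value is removed: 2/72 = 2.78% becomes 1/72 = 1.39%, a fall of 1.39 points.
- A flagged child leaves the table: 1/71 = 1.41%, a fall of 1.37 points.
- An unflagged child leaves the table: 2/71 = 2.82%, a rise of 0.04 points.

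With the baseline fixed, removing a post sample can only lower or leave unchanged the number of flagged children. The percentage can move either way.

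**The case against.** The case for leaving the rule alone has substance.

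- **The window is generous.** It is far wider than the schedule. No chemistry is scheduled later than 4 h after a procedure, so a 25-hour potassium or creatinine would be off-schedule. This stands, and it is why the loss may be small.
- **There is a rationale.** SAP 13.2.2 aims at changes that might be related to treatment, measured a few hours after baseline. This stands for the procedure-level tables. It does not explain why excluded results go uncounted and unlisted.
- **The baseline rules can be read together**, with 10.3.4.4 deciding eligibility and 10.3.1.1 choosing the last eligible value. That reading would settle the 12 h limit, but the SAP does not state it, and it does not settle the 15-minute allowance. Table 1 schedules no central-laboratory sample at screening, so an earlier baseline would seldom exist.
- **Opening the main tables to every later result has a cost.** Hematology is also taken around wound-management surgery, and a child with more samples has more chances of a flag. This stands, and it argues for a supplementary table.

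A reader might infer three stronger claims, and the documents support none of them:

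- *That affected children vanish from the laboratory harm tables.* The rule removes samples. Only the shift tables need a pair.
- *That the any-pCS percentages are too low.* Step 5 shows that the direction depends on who is lost.
- *That the arms are affected differently.* Table 1 sets the same pre-treatment timing for both arms. The samples required do differ by type of procedure, so a difference is possible, but nothing shows one.

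The adverse-event tables cannot be assumed to fill the gap, because the supplied text does not require significant laboratory values to be reported as adverse events.

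**Conclusion.** The point holds as a minor one about transparency and consistency. The filter reaches tables whose purpose it does not fit, it leaves no trace of what it removes, and it disagrees with 10.3.1.1 on which sample is baseline.

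Its size is unknown. The figures in step 4 rest on an assumed out-of-window rate and on both samples being due for all 145 children. For chemistry the base is smaller because of the 18 kg rule. With two procedures per child and a rate of 10% or less, fewer than 2 children would have no in-window post sample at all. The blood-loss sample-size calculation in SAP 13.3 allows for 30% missing values. Blood loss uses hematocrit before and after, so complete pairs were not expected there, but the causes are not stated and this is no estimate of out-of-window sampling.

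For rare findings one result can matter: in step 5 a single lost value halves a count of two. That is enough to justify an inexpensive safeguard, but not to doubt the planned main tables.

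**What to change.** Amend SAP 10.3.4.4 and 11.1.5.5 as follows.

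1. Keep the 12 h / 24 h window for procedure-level pre-post differences.
2. Reconcile 10.3.4.4 with 10.3.1.1. When no in-window value exists, let the last central-laboratory value before first treatment serve as baseline for the shift and pCS tables. State how a sample taken in the 15 minutes after start is to be treated.
3. Add a supplementary any-abnormal / any-pCS table and listing that include out-of-window post-treatment samples, marked as such, with samples around wound-management surgery shown separately.
4. Beside that table, report by arm the number of excluded samples and the number of samples per child.

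The cost is SAP wording, a changed data filter, and one extra table and listing with less uniform sampling times. The data are already held. PTT/INR is untouched and no clinical procedure changes.

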7.2.3.5. Laboratory Assessments

The following tests will be performed:

Serum chemistry, hematology and urinalysis testing will be performed at a central laboratory during NexoBrid eschar removal phase. Any additional procedures require hematology tests, as described in the protocol, will be performed using Central lab. Pregnancy testing, HbA1c, wound cultures, blood cultures and biopsies (if indicated) will be performed locally on-site.

The following tests will be performed in special central laboratories: Pharmacokinetics test, Immunogenicity evaluation.

Serum Chemistry:

Urea, Creatinine, Glucose, Total Bilirubin, Cholesterol, Triglycerides, Uric Acid, Total Protein, Albumin, Globulin, Calcium (Ca++), Phosphorous, Sodium (Na+), Potassium (K+), Chloride (Cl-), Alkaline Phosphatase, SGOT (ASAT), SGPT (ALAT), LDH.

Hematology:

Hemoglobin, Hematocrit, RBC, MCV, MCH, MCHC, Platelets, Leukocyte count (WBC) with differential count.

HbA1C² will be assessed at a local lab at Screening for diabetic patients as captured during the medical history.

Statistical Analysis Plan V02 of 31 May 2021

² HbA₁C will not be collected for patients weighing less than 18kg at screening

PTT and INR will be tested at a local lab pre treatment and post treatment.

Pregnancy Testing:

A serum or urine pregnancy (β HCG) test will be performed at a local lab for women of child bearing potential.

Urinalysis:

pH, Ketone, Specific gravity, Protein, Glucose, Bilirubin, Microscopic examination.

Qualitative Wound Culture:

Test burn wound for microbial flora (swab).

Blood Culture³:

Test blood for microbial flora

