Pain assessments will only be recorded while a subject is hospitalized. It may however be the case that certain subjects will be discharged during the first week, making some of the measurements not available. The respective subjects will be excluded from all pain analysis referring to time points after hospital discharge.

For each eschar removal procedure and each daily follow-up pain assessment the change in pain from baseline will be calculated as

$$Diff_d = Pain_d - Pain_{Base}$$

where $Pain_d$ is the pain assessment at the respective time point. For the calculation of the difference in pain for the eschar removal procedures the pain assessment post that procedure will be used. The pain value captured pre first procedure will be considered as baseline. If this is missing, the pain assessed at screening will be used.

In addition, for each patient, an indication will be produced whether:

- The patient experienced any post treatment abnormal (NCS) pain assessment according to investigator's assessment
- The patient experienced any post treatment abnormal (CS) pain assessment according to investigator's assessment

For subjects discharged before day 7, this indication will be calculated only taking into account the time during hospitalization.

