10.3.6. Laboratory Values

The following transformations will be applied to the central laboratory data obtained pre and post the eschar removal procedures:

Laboratory findings that are given in various units will be transformed to standard units. Laboratory values will be categorized as "abnormal (low)", "normal" and "abnormal (high)" based on the reference limits of the labs.

Pre-post differences of laboratory values for each eschar removal procedure will be calculated (difference between post-procedure value and pre-procedure value).

Absolute and relative frequencies of "abnormal (low)", "normal" and "abnormal (high)" findings will be calculated per laboratory value, eschar removal procedure and treatment arm.

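### Central-laboratory pCS is tabulated only as any post-baseline value, while samples per child follow the treatment pathway, so the by-arm rates are not comparable, in an unknown direction

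*SAP*

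**What the plan says.** SAP 10.3.4.4 (Central Laboratory Values) first classifies each measurement as pCS high, pCS low or neither, at each time point. It then collapses these to subject level: "for each subject and each laboratory parameter, an indication whether this subject experienced any pCS high measurement post baseline in this parameter", and the same for low values. There is no cap on the number of samples and no time window.

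Section 11.1.5.5 reports the result in one form: "Additional tables will indicate shifts from baseline (low/normal/high) to any post treatment potentially clinically significant result", with a listing of the children concerned. The denominator for shift tables is tied to having a value before and after the procedure in question, which has no clear meaning for a table pooled over procedures.

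Sampling is tied to procedures. Section 10.3.6 speaks of "central laboratory data obtained pre and post the eschar removal procedures". Section 10.3.4.4 accepts samples from 12 hours before to 15 minutes after the start of a procedure, or within 24 hours after its end, and adds: "Samples not taken in the allowed time range are excluded from the analysis". Not every procedure brings a sample: "a laboratory sample before a nonsurgical procedure is only prescribed for the first eschar removal procedure", the post-sample of a non-surgical procedure is required only when it is the last, and a repeat NexoBrid application needs no pre-sample. A footnote to Table 1 limits chemistry to baseline in children under 18 kg.

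**The concern.** An any-value flag rises with the number of values examined. Here that number is set by the pathway after randomization. In the sponsor's earlier trials the pathway differed strongly by arm: surgical excision occurred in 0.42 (NexoBrid) versus 0.80 (SoC) of patients in MW2004-11-02 and in 0.04 versus 0.72 in MW2010-03-02 (SAP 13.3). The SAP also expects repeat surgery, since 11.1.5.5 has a category for additional surgical procedures.

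Appendix 13.2.2 explains that pCS thresholds combine a value with a change from baseline because burn patients may have abnormal laboratory results before treatment. The pCS table is thus the display meant to pick up treatment-related change. If its two columns rest on different numbers of looks, a difference between arms may be an artefact and a true difference may not show.

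The SAP handles other safety data differently. Vital-sign pCS is shown at each of the first seven daily assessments, and its any-result table is restricted to those days and repeated without early discharges (11.1.5.6). INR/PTT pCS uses one sample, after first treatment, in both arms (11.1.5.14). Central-laboratory pCS has no fixed-time version.

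**Working it through.** **No figure to reproduce on this point.** The documents give no pCS rates and no samples per child. As a check on the excision inputs, the Fisher power for 0.44 versus 0.78 with 80 per arm was recomputed by full enumeration: 99.2%, against 99.1% in SAP 9.1.2.

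**Step 1: required post-baseline samples, k** (Table 1 and 10.3.4.4). The pre-sample of the first procedure is the baseline.

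- NexoBrid alone: k = 1.
- NexoBrid, then one surgery: k = 3 (after NexoBrid, before surgery, after surgery).
- SoC, non-surgical only: k = 1.
- SoC, s surgeries: k = 1 + 2(s − 1), that is 1, 3 or 5 for s = 1, 2 or 3.
- SoC, non-surgical start then one surgery: k = 2.

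**Step 2: formula.** With per-sample flag probability p and independent samples, P(any) = Σ w × [1 − (1 − p)^k], where w is the share of children on each pathway. Excision rates are from SAP 13.3. The value of p, the number of surgeries and independence are assumptions.

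**Step 3: p = 5%, same true risk in both arms.** The building blocks are 0.0500 (k = 1), 0.0975 (k = 2), 0.1426 (k = 3) and 0.2262 (k = 5).

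- MW2010-03-02 rates, two surgeries. NexoBrid: 0.96 × 0.0500 + 0.04 × 0.1426 = 5.4%. SoC: 0.28 × 0.0500 + 0.72 × 0.1426 = 11.7%.
- MW2004-11-02 rates, one surgery. NexoBrid: 0.58 × 0.0500 + 0.42 × 0.1426 = 8.9%. SoC: k = 1 for all, 5.0%.

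The break-even ratio is the per-sample risk ratio (NexoBrid/SoC) at which the two any-pCS rates are equal.

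| Excision rates | Operated SoC child | Mean samples, NexoBrid vs SoC | Any pCS, NexoBrid vs SoC | Break-even ratio |
|---|---|---|---|---|
| MW2010-03-02 | one surgery | 1.08 vs 1.00 | 5.4% vs 5.0% | 0.93 |
| MW2010-03-02 | non-surgical, then one | 1.08 vs 1.72 | 5.4% vs 8.4% | 1.57 |
| MW2010-03-02 | two surgeries | 1.08 vs 2.44 | 5.4% vs 11.7% | 2.19 |
| MW2010-03-02 | three surgeries | 1.08 vs 3.88 | 5.4% vs 17.7% | 3.33 |
| MW2004-11-02 | one surgery | 1.84 vs 1.00 | 8.9% vs 5.0% | 0.55 |
| MW2004-11-02 | non-surgical, then one | 1.84 vs 1.80 | 8.9% vs 8.8% | 0.99 |
| MW2004-11-02 | two surgeries | 1.84 vs 2.60 | 8.9% vs 12.4% | 1.42 |
| MW2004-11-02 | three surgeries | 1.84 vs 4.20 | 8.9% vs 19.1% | 2.24 |

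Over p from 2% to 10%, and including a non-surgical start before two or three surgeries, the ratio runs from 0.55 to 4.10.

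**Step 4: sensitivity.** If only post-procedure samples count, the two worked cases become 5.2% vs 8.4% and 7.0% vs 5.0%: smaller, with the same opposite directions. Within-child correlation also shrinks the gap; with perfect correlation both arms show 5.0%. Not modelled are a second NexoBrid application and the hematology that Table 1 draws around wound-management surgery.

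**Step 5: one fixed sample per child.** At the sample after the last eschar removal procedure k = 1 in both arms. No effect gives 5.0% vs 5.0%, and a doubled per-sample risk on NexoBrid gives 10.0% vs 5.0%.

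**The case against.** The strongest reply is that other displays already cover this. Section 11.1.5.5 shows values, pre-post differences and low/normal/high categories by arm, for each procedure and at the last one. The comparison from before the first to after the last procedure gives one look per child. Children with pCS shifts are listed, and adverse events are tabulated separately. This stands in part: a harm would not vanish from the report. But these summaries do not apply the pCS criteria, and the by-type tables do not align the arms, since a first application exists only for NexoBrid.

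A second reply is that extra surgery may itself cause, for example, low hemoglobin, so a higher SoC rate could be a real consequence of the strategy. That is fair, but the any-pCS table cannot separate it from the effect of more samples.

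A reader might infer that SoC children have more procedures and hence more looks, so that the table favours NexoBrid and hides harm. The documents do not support this. Excision incidence is not a sample count. Intermediate non-surgical sessions add no required sample. An SoC child with one excision has one post-baseline sample, against three for a NexoBrid child who later needs surgery.

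A reader might also extend the point to pain, where 10.3.4.4 flags whether "The patient experienced any post treatment abnormal (CS) pain assessment". That does not hold: 11.1.5.7 already shows shifts from baseline separately at each time point. INR/PTT is likewise unaffected.

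**Conclusion.** The point holds in limited form. By-arm any-pCS rates for central-laboratory parameters are not comparable, because the number of countable samples follows the treatment pathway and no pCS table gives each child one look. The size depends on assumed surgery counts, an assumed per-sample risk and independence between samples. Depending on the surgery counts and on which earlier trial's excision rates apply, equal risk could appear as 5.4% vs 11.7% or as 8.9% vs 5.0% (NexoBrid vs SoC). Neither a bias in the sponsor's favour nor a fully hidden harm can be claimed.

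The scope is mainly hematology, plus chemistry at 18 kg or more. Of the 145 children, 45 + 30 = 75 are aged up to 3 years (SAP 13.3); how many weigh under 18 kg is not stated. The laboratory tables are descriptive, so no error rate or power figure changes. The change is still worth making, because it is cheap and these tables are where laboratory safety is read by arm.

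**What to change.** In SAP 11.1.5.5:

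1. Add, by arm, a shift table from baseline to pCS low/high at the sample after the last eschar removal procedure. Every pathway requires this sample, and the pCS variable already exists for each time point.
2. Keep the any-pCS table. Beside it, show the number of post-baseline samples per child by arm and the per-sample pCS rate (pCS samples divided by samples evaluated, with the child as cluster).
3. Define the denominator of the any-pCS table, for example children with a baseline and at least one post-baseline value. State whether hematology around wound-management surgery counts.
4. Optionally add a table after the first procedure as supportive. Note that it will be missing for children whose first procedure is non-surgical and not the last, so it should not be the main comparison.

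The cost is some SAP wording and a few descriptive tables from existing data, with no new samples. One limit remains: the time from baseline to the last procedure may differ between arms.
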